## 8. SUBJECT ELIGIBILITY AND WITHDRAWAL CRITERIA

### 8.1 Inclusion Criteria

Subjects fulfilling all of following criteria may be eligible for study participation.

1. Subject has signed and dated the ICF prior to any study-related procedure not part of normal medical care;
2. Subject is aged 18 years or older and is able and willing to comply with the contraception requirements described in Section 12.7.2;
3. Subject at the Screening and Day 1 Pre-Dose Visits has a minimum of 4 and a maximum of 8 discrete Grade 1-2 AK (see AK Grades, Section 11.1.1) lesions within a single 25 cm^2 area of skin on their scalp or face that meet the criteria for the AK Lesions and Treatment Field listed in Sections 11.1.2 and 11.1.3, respectively.
4. Subject (or their dosing partner) has demonstrated adequate precision applying the study drug to the Treatment Field during the Screening and Day 1 Pre-Dose Visits.

### 8.2 Exclusion Criteria

Subjects fulfilling any of the following criteria will be excluded from study participation:

1. Subject is the PI or any Sub-Investigator, research assistant, pharmacist, Study Coordinator, staff directly involved in the trial, and/or any immediate family member (first degree relative, spouse, adoptees, legal dependents) of any staff directly involved in the trial;
2. Subject has screening results that (a) are clinically significant and have not been approved in writing by the Safety Monitor; (b) suggest an unstable medical condition; (c) preclude the subject's participation out of concern for the subject's safety; or (d) suggest a condition that might confound the subject's data.
3. Subject is: (a) pregnant; (b) lactating; (c) planning to become pregnant during the study, or (d) fertile (as defined in Section 12.7.1) and they or their fertile partner is unable or unwilling to use the contraceptive methods discussed in Section 12.7.2;
4. Subject has any skin pathology, known dermatologic disease, or medical condition that could interfere with the evaluation of the test product or requires the use of an interfering topical or systemic therapy;
5. Subject is immunosuppressed (e.g., organ transplant recipients, HIV, systemic chemotherapy, graft vs. host disease, receiving dialysis, etc.);
6. Subject is currently enrolled in a clinical trial or has received an investigational drug or been treated with an investigational device within 21 days prior to Screening.

7. Subject is unable to comply with the sun protection techniques or the limitations placed on tanning, medicinal products, activities, or foods listed in Section 12.6;
8. Subject has (a) an unstable medical, psychiatric, or social problem; (b) self-reported alcohol or illicit drug dependency; (c) communication or motor deficit; or (d) any similar condition that could place the subject at a safety risk or might interfere with the performance of the trial activities, completion of the trial, and/or interpretation of the subject's data or risk the safety of the subject.
9. Subject may be unreliable for the study including subjects who engage in excessive alcohol intake or drug abuse, or subjects who are unable to return for scheduled follow-up visits.
10. Subject has a known sensitivity to propylene glycol, caprylic acid, dimethyl sulfoxide (DMSO), petrolatum, or paraffin wax.
11. Subject is unwilling to avoid any form of therapy, emollients, moisturizers, makeup, sunscreens, etc. to the Treatment Field from Screening through Day 84 except for bland emollients prescribed by the site Investigator.
12. Subject has used any of the following topical treatments in the Treatment Field:
  - Topical retinoids (e.g. tazarotene, adapalene, tretinoin) within 8 weeks of Screening, or
  - Microdermabrasion, laser ablative treatments, ALA-PDT, chemical peels, 5-FU, diclofenac, imiquimod, ingenol, or other topical treatments for AK or that might impact AK within 12 weeks of Screening.
13. Subject has used systemic retinoid therapy within 6 months of Screening Visit.
14. Subject has a history of malignancy within 5 years of Screening other than adequately-treated carcinoma in-situ of the cervix and non-metastatic basal cell or squamous cell carcinoma of the skin.
15. Subject had major surgery within 60 days of Day 1 or plans to have major surgery during the study; or
16. Subject has any reason that will preclude repeated venipuncture.

***Additional Exclusion Criteria for Subjects in the PK Study Sub-Cohort:***

17. Subject has a Body Mass Index (BMI) of  $\leq 18$  and  $\geq 35$ ;
18. Subject within 4 weeks of Screening had major blood loss or donated blood or a blood component;

19. Subject has any clinically significant medical abnormality or chronic disease that may interfere with the absorption, metabolism, or excretion of the investigational product. This includes such conditions as hepatic, renal, cardiac, or pulmonary disease or an estimated glomerular filtration rate <60 milliliters per minute;
20. Subject (self-reported) abused drugs or alcohol within 3 years of screening or used tobacco, smoking cessation products, or products containing nicotine within three months of Screening;
21. Subject has positive toxicology or drug, at Screening other than a benzodiazepine for sleep that the subject is willing to avoid during the trial and is negative upon re-test during Screening;
22. Subject is unable or unwilling avoid alcoholic beverages, smoking, nicotine products, and any medications unapproved by the Investigator from Screening through Day 35; or
23. Subject was exposed to any paint solvents or pesticides within 4 weeks of Screening.

### **8.3 Subjects Withdrawn, Terminated, or Lost to Follow-Up**

Subjects who are terminated by the PI, who withdraw from the study, or who are lost to follow-up and who received at least one dose of the study drug will not be replaced.

### **8.4 Subject Withdrawal**

Subjects may withdraw their consent at any time and for any reason.

Subjects who have applied at least 1 study drug dose and would like to withdraw from the study will be offered to attend all of the scheduled study visits and to undergo the planned safety and efficacy assessments.

### **8.5 Subjects Leaving the Trial**

#### **8.5.1 Termination by the Investigator**

The Investigator may terminate a subject from the study at any time, due to: (a) trial misconduct, (b) violation of the rules of the site, (c) protocol violation; (d) pregnancy, or (e) unexpected personal issues that arose during the trial.

Subjects who have applied at least 1 dose of the study drug and are terminated from the study will be asked to attend all of the scheduled study visits through Day 84, as appropriate.

If an Investigator (or designee) is of the opinion that continued daily dosing may be detrimental to a subject's well-being, that subject may be offered the options discussed in Section 7.6 (Dose Holidays and Adjustments) following consultation with the Safety Medical Monitor.

### **8.5.2 Subjects Who Wish to Withdraw**

If a subject who received at least 1 dose of the study drug wishes to withdraw from the trial, study staff should ask the subject to complete as many as possible of the planned evaluations scheduled through Day 84, as appropriate. If the subject declines, the subject should be asked to undergo the Day 28 safety and efficacy procedures.

Subjects may also be offered the options listed in Section 7.6.

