## 7.7 Study Endpoints

**Primary Efficacy Endpoint:** Change from baseline in the number of AK lesions within the Treatment Field of each subject on Day 56.

**Safety Endpoints:** Assessment of AEs, vital signs, physical examinations, clinical laboratory parameters, Local Skin Reaction (LSR) Scores, and electrocardiograms.

**Pharmacokinetic Endpoint:** Assessment of the systemic exposure of VDA-1102 and its primary metabolite jasmonic acid at selected time points during topical application of 5% or 10% VDA-1102 ointment for 28 days in adult subjects with AK.

**Exploratory Endpoints:** The percentage of subjects achieving complete clearance of AK lesions within the Treatment Field on Day 56.

Change from baseline in the number of AK lesions within the Treatment Field of each subject on Day 84.

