- Study Drug Measurement and Application review (see Section 13.6.3)
- Study drug accountability and dosing compliance: study drug tubes will be weighed, the results recorded, and diaries reviewed and photocopied
- Study drug and study tools will be given to the subject, as needed

The following additional procedures will be performed on the Day 14 Visit only in subjects enrolled in the subjects enrolled in the PK Study Sub-Cohorts:

- ❖ PK blood sampling approximately 12 hours after the Day 13 dose
- Subject Instruction Packet will be reviewed including an appointment for the next visit will be given
- ✓ **Day 14 through Day 27**
  - Subjects will dose at home each evening approximately 2 hours before bedtime and record the application in the Dosing Diary.
  - Site personnel will communicate with the subjects once a week (Section 10.1.6) in order to review the Subject Instruction Packet and Dosing Diary as well as to remind each subject of their next site visit
- ✓ **Day 28 Visit**

On Day 28 ( $\pm 4$ ) the following procedures will be performed:

- Adverse event(s) AEs will be recorded
- Concomitant medications documented
- Vital signs: peripheral blood pressure, respiratory and heart rates, and oral temperature will be recorded
- Physical examination
- Local Skin Reaction Score in the Treatment Field
- AK Lesions in the Treatment Field: count (11.1.5) and grading (11.1.1)
- Study drug accountability and dosing compliance: study drug tubes will be weighed and the results recorded. Dosing Diaries will be collected and not returned

- 12-lead ECG tracing recorded as per the ERT manual. An original (duplicate) copy of each ECG is required. This ECG will also be transmitted to the central ECG laboratory
- Complete clinical laboratory tests: Fasting status to be recorded
- Urine pregnancy test will be performed at the investigative site in all females and the results will be recorded

The following Procedure will only be performed on the Day 28 Visit in subjects enrolled in the **PK Study Sub-Cohort**:

- ❖ PK blood sampling approximately 12 hours after the Day 27 dose. Additional blood samples will be collected at approximately 15, 18, and 21 hours post dose
- ❖ 24-hour ambulatory cardiac Holter monitor will be connected to the subject
- Trial instruction review including an appointment for the next visit will be given.

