#### 12.4.3 Observation Period

✓ ***Day 29 through Day 34***

- No procedures will be performed on these days.
- ❖ Subjects in the **PK Study Sub-Cohort** will remove the Holter on Day 29 approximately 24 hours after it was attached and will be returned by the subject to the site on Day 35.

✓ ***Day 35 Visit***

On Day 35 ( $\pm 2$ ) the following procedures will be performed:

- Adverse event(s) will be recorded
- Concomitant medications documented
- Vital signs: peripheral blood pressure, respiratory and heart rates, and oral temperature will be recorded
- Physical examination
- Local Skin Reaction Score in the Treatment Field
- AK Lesion in the Treatment Field: count (11.1.5) and grading (11.1.1)
- Trial instruction review including appointment for the next visit will be given

The following Procedure will only be performed on the Day 35 Visit in subjects enrolled in the PK Study Sub-Cohort:

❖ PK blood sampling

✓ ***Day 36 through Day 55***

From Day 36 through Day 55 no procedures will be performed.

✓ ***Day 56 Visit***

On Day 56 ( $\pm 4$ ) the following procedures will be performed:

- Adverse event(s): volunteered, elicited, and observed AEs will be recorded
- Concomitant medications documented
- Local Skin Reaction Score in the Treatment Field
- AK Lesions in the Treatment Field: count (11.1.5) and grading (11.1.1)
- Urine pregnancy test will be performed in all females and the results will be recorded
- Photographs of Treatment Field at selected sites
- Trial instruction review including appointment for the next visit will be given

✓ ***Day 57 through Day 83***

From Day 57 through Day 83 no procedures will be performed

✓ ***Day 84 Visit***

On Day 84 ( $\pm 4$ ) the following procedures will be performed:

- Adverse event(s): volunteered, elicited, and observed AEs will be recorded
- Concomitant medications documented
- Local Skin Reaction Score in the Treatment Field
- AK Lesions in the Treatment Field: count (11.1.5) and grading (11.1.1)
- Photographs of Treatment Field at selected sites
- Visit Closure Procedures: Subjects will be thanked for their participation and completion of the study will be noted in the subject's record

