#### 17.2.1 Efficacy Analysis

The efficacy analysis will be performed with the ITT, mITT, and PP populations (see Section 17.5.2). The primary efficacy endpoint is the change from baseline in number of AK lesions. If the baseline lesions number will be found different between the treatment groups, then relative change (%) will be analyzed as well. The within-group absolute changes (decrease) in AK number of lesions from baseline to each visit will be analyzed using paired t-test or signed rank test for two means (paired observations, as is appropriate).

Comparative analysis of the above changes will be applied between each of the active groups versus the placebo group using the two-sample t-test, the non-parametric Wilcoxon-Mann-Whitney rank sum test for independent samples, or the Median test (as appropriate).

If no statistically significant differences are observed between the two active VDA-1102 groups then these two groups will be pooled and compared to the placebo group in order to achieve higher statistical power.

The overall effect and trend of differences in the changes over time between the groups will be analyzed using a mixed-effect model for repeated measures. The model will include changes from baseline at any time, the fixed effect time, and the interaction of treatment and time. Contrast will be calculated for each time point (Days 7, 14, 28, 35 and 56) versus baseline and the overall effect. The model will be adjusted for baseline measure and for other covariates suspected as affecting the outcome and which will be found different between the treatment groups.

In case the baseline number of lesions differs between the groups, analysis of relative change (%) will be applied as well.

Chi-square test or Fisher's exact test (as is appropriate) will be used for analyzing the difference in percent of subjects with complete clearance of study AK lesions at the end of the treatment. Logistic regression will be applied for analyzing the difference in proportions with adjustment for baseline measure and for other covariates suspected as affecting the outcome and which will be found different between the treatment groups.

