#### 5.4.4 Handling of Missing Data

5.4.4.1 Assuming the scope of missing data of the primary efficacy endpoint will be significant, data imputation will be applied. Missing data at random imputation (MAR) will be performed for those subjects with missing efficacy data. Multiple imputation will be applied using SAS PROC MI to perform the imputations. Sensitivity analysis will be used for detecting differences between the analyses with and without data imputation.

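### For a withdrawing subject who declines further visits, the fallback request is the Day 28 procedure set, not a lesion count at Day 56, the only time point of the primary endpoint

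*Protocol*

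**What the plan says.** Protocol 8.5.2 handles withdrawal in two steps. First, "study staff should ask the subject to complete as many as possible of the planned evaluations scheduled through Day 84, as appropriate". Then: "If the subject declines, the subject should be asked to undergo the Day 28 safety and efficacy procedures". SAP 5.6.2.3.1 carries the same two steps. Protocol 8.4 adds that subjects who have applied at least one dose and want to withdraw "will be offered to attend all of the scheduled study visits and to undergo the planned safety and efficacy assessments".

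The primary endpoint (Protocol 7.7) is "Change from baseline in the number of AK lesions within the Treatment Field of each subject on Day 56". SAP 5.6.5.2 places the between-group comparison at Day 56.

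If the Day 56 count is missing, SAP 5.4.4 says: "Assuming the scope of missing data of the primary efficacy endpoint will be significant, data imputation will be applied". The method is multiple imputation under missing at random. No level of missingness is given that would trigger it. The only sensitivity analysis compares results with and without imputation. SAP 5.6.2.1.1 limits change-from-baseline tabulations to subjects with both a baseline and a follow-up value. SAP 5.5.2.3 and 5.5.3.3 limit the mITT and PP analyses at Day 56 to subjects who completed Day 56.

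For the repeated-measures model, Protocol 17.2.1 says: "Contrast will be calculated for each time point (Days 7, 14, 28, 35 and 56) versus baseline and the overall effect". SAP 5.6.5.6 lists Days 7, 14, 28 and 56.

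**The concern.** Once a subject has turned down the remaining schedule, sites make one more request, and it names Day 28. The Day 28 set does include a lesion count, but that count is not a Day 56 value and neither document lets it stand in for one. A subject prepared to do one more thing is therefore not asked, at that point, for the observation that the primary test uses.

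What is at stake is avoidable missing primary data in a group whose absence may be related to treatment, for example through a skin reaction or lack of effect. That link is a reasonable worry; the documents do not establish it. An observed Day 56 count needs no missing-data assumption. The planned imputation does, and no analysis tests departure from missing at random.

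A smaller, related gap is that neither document says when the fallback procedures take place or to which visit an exit count belongs. The derived-data rules in SAP 5.6.2 define baseline, end of study, early termination and incomplete dates, but no visit assignment.

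**Working it through.** **1. Which request covers Day 56**

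| Situation | Request | Day 56 count covered? |
|---|---|---|
| Wishes to withdraw (8.4) | All scheduled visits offered | Yes |
| Wishes to withdraw, first step (8.5.2) | As many evaluations through Day 84 as possible | Yes, not singled out |
| Declines that (8.5.2, second step) | Day 28 procedure set | No |

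The gap is confined to the last row.

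**2. Content of the two visits (Protocol 12.4.2 and 12.4.3).** Day 28 lists vital signs, physical examination, ECG, laboratory tests, skin reaction score and lesion count. Day 56 lists a lesion count and skin reaction score but no ECG, laboratory tests or physical examination. A count-only visit at Day 56 would be lighter than the visit now requested.

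**3. The plan's own figures.** Inputs from Protocol 17.1: effect size d = 0.83, two-sided alpha 0.045, two-group t-test, 25 per group, 10% drop-out. Power comes from the noncentral t distribution with df = n1 + n2 − 2 and noncentrality d × √(n1·n2/(n1+n2)).

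- 25 per arm: df = 48, noncentrality 0.83 × √12.5 = 2.93, critical value 2.06, power 80.7%. The stated 80% is reproduced, and 25 is the smallest equal group size that reaches it.
- Recruitment: 75/0.9 = 83.3, rounded up to 84, also reproduced.
- Planned loss: 84 − 75 = 9 subjects, 3 per arm, 9/84 = 10.7%.

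**4. Value of recovered Day 56 counts**

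| Observed at Day 56 (active, placebo) | Power |
|---|---|
| 25, 25 | 80.7% |
| 26, 25 | 81.5% |
| 26, 26 | 82.3% |
| 27, 27 | 83.8% |
| 28, 28 | 85.1% |

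One recovery in one arm adds 81.5 − 80.7 = 0.8 points. One in each compared arm adds 82.3 − 80.7 = 1.6 points, and the average over the three steps is (85.1 − 80.7)/3 ≈ 1.5. In the other direction, 24 per arm gives 79.0%, so there is little slack beyond the planned loss.

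**5. Where an exit count would fall.** The post-baseline windows in the schedule are Days 5–9, 12–16, 24–32, 33–37, 52–60 and 80–88. Two illustrative exits, on Day 10 and Day 40, fall in none of them. If such a count were labelled Day 28, it would enter the Day 28 contrast of the repeated-measures model 18 days early or 12 days late. No text directs that labelling, and none prevents it.

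**The case against.** The strongest reply is that Day 56 has already been requested. The first step in 8.5.2 is flexible: a subject willing to make a single later visit can agree to Day 56 under it. Protocol 8.4 offers every visit, 8.5.1 asks terminated subjects to attend through Day 84, and 8.5.2 points to the options in 7.6, one of which is to stop study drug and otherwise be followed as planned. A reader might infer from the fallback that a decliner is never asked for a Day 56 count. The documents do not support that. What remains is that the first step does not single out Day 56, and the second step names a different visit.

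The Day 28 set also has an evident use as a full exit assessment, including ECG and laboratory tests. That stands, and it is a reason to add to the fallback and not to replace it.

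On size, the 3 per arm include loss to follow-up and termination by the investigator, so decliners are only part of them. Some will refuse a repeated request, and the yield may be near zero. A reader might take the full step from 80.7% to 85.1% as the expected gain. It is a ceiling that requires every planned loss in both arms to be recovered. A subject who leaves on Day 10 would also have fewer than 20 dosing days, a major deviation under SAP 5.4.5.2.1.2, and would stay out of the PP analysis even with a Day 56 count. The count would still serve the ITT analysis.

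A reader might also infer that exit counts will be stored as Day 28 and distort that estimate. No passage says so, and the Day 28 wording can be read as describing content only. This part is a conditional gap in the SAP and does not touch the Day 56 between-group comparison.

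**Conclusion.** The point holds as a modest one. For subjects who withdraw and decline the remaining schedule, both documents fall back to a request that does not target the only time point of the primary endpoint, and nothing later replaces the lost value except a conditional imputation under missing at random. The benefit of changing this is fewer missing primary values: at most 3 per arm, worth about 0.8 points of power for one recovery in one arm and about 1.5 for one in each compared arm.

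These figures assume the plan's effect size of 0.83, its two-sided 0.045 level and an analysis of observed counts. The share of decliners who would accept one visit is not given; the range is 0 to 3 per arm. The reduction in possible bias cannot be quantified from the documents and matters more than the power.

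This is not a sample size error. The 10% drop-out allowance is already in N = 84, and the stated 80% power stands.

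**What to change.** - **Protocol 8.5.2 and SAP 5.6.2.3.1:** keep the exit safety assessment and lesion count at the time of leaving, and state that timing. Add that a subject who declines the remaining schedule will be asked, as the priority, to return once at Day 56 ±4 for the AK lesion count only.
- **SAP 5.6.2:** assign any exit count to the visit window that contains its actual study day, not by the label Day 28. A count outside every window is not analysed as Day 28. It is kept, with its actual day, as information for the multiple imputation. The SAP should say in what form it enters the imputation model, since few other subjects will have a count on such a day.

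Simply listing out-of-window counts would be a poorer rule, because it would discard late observed values such as the Day 10 and Day 40 examples.

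The cost is one sentence in each document, one visit-assignment rule in the SAP, and one further voluntary request to a few subjects, many of whom may refuse. No new procedure is needed, and no stated figure changes.
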